| | Daratumumab | 16 mg/kg | Every week (Wks 1-8) then every 2 weeks (Wks 9-24), then every 4 weeks starting at Week 25 | Intravenous (IV) infusion See Section 4.3 | |

^a A delay of the 2nd dose of nivolumab is acceptable for up to 1 week (up to Day 22); however, the 2nd dose of nivolumab should not be administered after Day 22 in order to avoid postponing surgery/biopsy beyond Day 29 and subsequent standard of care.

Study Assessments:

Safety:

Safety assessments at baseline will include a medical history to be obtained to capture relevant underlying conditions. Baseline examinations should include signs and symptoms, weight, height, ECOG Performance Status, BP, HR, temperature, and respiratory rate should be performed within 14 days prior to first dose. Concomitant medications will also be collected from within 14 days prior to first dose and through the study treatment. Baseline safety laboratory assessments should be done within 14 days prior to the first dose.

Subjects will be evaluated for safety if they have received any study drug. Toxicity assessments will be performed continuously during the treatment phase. On-study assessments including weight, height, ECOG Performance Status, BP, HR, temperature, respiratory rate, and oxygen saturation by pulse oximetry at rest and after exertion will be performed. On-study safety laboratory assessments will also be performed.

Efficacy:

Tumor imaging assessments for ongoing study treatment decisions will be completed by the investigator using RECIST (Response Evaluation Criteria in Solid Tumors) 1.1 criteria.

Statistical Considerations:

Sample Size: Sample size determination is not based on statistical power calculation.

1) Neoadjuvant cohort:

The SCCHN tumor types will contain 21 HPV-positive and 21 HPV-negative evaluable subjects. MCC and cervical, vaginal, or vulvar cancers tumor types will contain 21 evaluable subjects each. A sample size of 21 subjects can detect, with more than 66% and 89% probability, a safety event that occurs at an incident rate of 5% and 10%, respectively. Assuming 10%, 15%, and 20% for pathologic complete response rate, a sample size of 21 can detect, more than 89%, 97% and 99% probability, at least one pathologic complete response respectively.

2) Recurrent/metastatic monotherapy cohort:

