1.2 Research Hypothesis

Research Hypothesis (A): Nivolumab, in the neoadjuvant setting, will be safe and tolerable in subjects with select virus positive and virus-negative tumors.

Research Hypothesis (B): Treatment with nivolumab alone or in combination with either ipilimumab, BMS-986016 (relatlimab), or daratumumab will lead to clinically meaningful tumor reductions, as measured by objective response rate and duration of response, in subjects with metastatic or unresectable tumors.

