8 STATISTICAL CONSIDERATIONS

8.1 Sample Size Determination

- Sample size determination is not based on statistical power calculation.

1) Neoadjuvant cohort:

The SCCHN tumor types will contain 21 HPV-positive and 21 HPV-negative evaluable subjects. MCC and cervical, vaginal, or vulvar cancers tumor types will contain 21 evaluable subjects each. A sample size of 21 can detect, with more than 66% and 89% probability, a safety event that occurs at an incident rate of 5% and 10%, respectively. Assuming 10%, 15%, and 20% for pathologic complete response rate, a sample size of 21 can detect more than 89%, 97% and 99% probability, at least one pathologic complete response respectively.

2) Recurrent/metastatic monotherapy cohort:

HPV+ SCCHN, GYN, MCC and NPC tumor types in the recurrent/metastatic cohort will contain approximately 23 subjects. Table 8.1-1 shows the probabilities of observing 0, 1 or 2 responders and ≥ 3 responders assuming 5%, 20% and 30% true response rate of ORR. Table 8.1-2 shows the two-sided 95% exact CI using Clopper-Pearson methods based on observed 3, 4 and 5 responders out of 23 subjects.

EBV+ Gastric tumor type will contain approximately 12 subjects, due to the low prevalence. Table 8.1-5 shows the precision of the estimation of ORR based on the two sided 95% exact CI using Clopper-Pearson methods based on 1, 2, 3, 4 and 5 responders out of 12 subjects.

Table 8.1-1: Probability of Observing Responses Given True ORR for Sample Size of 23 Subjects

| True ORR | Probability of observing 0, 1 or 2 responses | Probability of observing ≥ 3 responses |
|----------|--|---|
| 5% | 89.5% | 10.5% |
| 20% | 13.3% | 86.7% |
| 30% | 1.6% | 98.4% |

Table 8.1-2: Two-sided 95% Exact CI Using Clopper-Pearson Method Based on Number of Observed Responses out of 23 Subjects

| The number of observed responses | 3 | 4 | 5 |
|----------------------------------|---------------|---------------|---------------|
| Observed Response Rate | 3/23 (13.0%) | 4/23 (17.4%) | 5/23 (21.7%) |
| 95% exact CI | (2.8%, 33.6%) | (5.0%, 38.8%) | (7.5%, 43.7%) |

3) Recurrent/metastatic combination cohort:

The HPV+ SCCHN, MCC, and NPC tumor types in the recurrent/metastatic cohort will each contain approximately 40 subjects that will be enrolled to the Combo A treatment arm. Patients with cervical cancer and anogenital HPV associated tumors (vulvar/vaginal/anal canal/penile) tumor types will be randomized in a 1:1 ratio to one of two dosing schema (Combo A or Combo B).

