8.4.2 Efficacy Analyses

8.4.2.1 Primary Endpoint Methods

Neoadjuvant cohort:

- Analyses of drug-related select AEs and drug-related SAEs are discussed in [Section 8.4.3](#)
- Rate of surgery delay will be summarized by binomial response rates and their corresponding two-sided 95% exact CIs using Clopper-Pearson method.

Metastatic cohort (monotherapy and combination therapies):

- The investigator assessed ORR in the metastatic cohort will be summarized by binomial response rates and their corresponding two-sided 95% exact CIs using Clopper-Pearson method.

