8.4.2.2 Secondary Endpoints Methods

Metastatic cohort (monotherapy and combination therapies):

- Time to event distribution will be estimated using Kaplan Meier techniques. This will be done for PFS (based on investigator assessments) and OS. Median PFS or OS along with 95% CI will be constructed based on a log-log transformed CI for the survivor function. Rates at some fixed time points will be derived from the Kaplan Meier estimate and corresponding

confidence interval will be derived based on Greenwood formula for variance derivation and on log-log transformation applied on the survivor function.

- The DOR will be summarized for all treated subjects who achieve confirmed PR or CR using the Kaplan-Meier (KM) product-limit method. Median values of DOR, along with two-sided 95% CI using Brookmeyer and Crowley method, will also be calculated.

8.4.2.3 *Exploratory Endpoints Methods*

Methods for exploratory endpoints will be discussed in detail in the statistical analysis plan.

8.4.3 *Safety Analyses*

Safety analyses will be performed in all treated subjects. Descriptive statistics of safety will be presented using NCI CTCAE version 4. All on-study AEs, drug-related, AEs, SAEs and drug-related SAEs will be tabulated using worst grade per NCI CTCAE version 4 criteria by system organ class and MedDRA preferred term. On-study lab parameters including hematology, chemistry, liver function, thyroid function, and renal function will be summarized using worst grade per NCI CTCAE version 4 criteria.

The proportion of subjects in the neoadjuvant cohort with surgery delayed > 4 weeks due to a drug-related AE will be reported for each tumor type and the Clopper-Pearson method will be used to estimate the two-sided 95% confidence interval.

8.4.4 *Pharmacokinetic Analyses*

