5 SAMPLE SIZE

Sample size determination is not based on statistical power calculation.

1) Neoadjuvant Cohort:

The SCCHN tumor types will contain 21 HPV-positive and 21 HPV-negative evaluable subjects. MCC and HPV positive cervical, vaginal, or vulvar cancers tumor types will contain 21 evaluable subjects each. A sample size of 21 can detect, with more than 66% and 89% probability, a safety event that occurs at an incident rate of 5% and 10%, respectively. Assuming 10%, 15%, and 20% for pathologic complete response rate, a sample size of 21 can detect, more than 89%, 97% and 99% probability, at least one pathologic complete response respectively.

1) Recurrent/Metastatic Monotherapy Cohort:

HPV+ SCCHN, GYN, MCC and NPC tumor type in the recurrent/metastatic cohort will contain 23 subjects. Table 5-1 shows the probabilities of observing 0, 1 or 2 responders and \square 3 responders assuming 5%, 20% and 30% true response rate of ORR. shows the two sided 95% exact CI using Clopper-Pearson methods based on observed 3, 4 and 5 responders out of 23 subjects.

EBV+ Gastric tumor type will contain approximately 12 subjects, due to the low prevalence. Table 5-3 shows the precision of the estimation of ORR based on the two-sided 95% exact CI using Clopper Pearson methods based on 1, 2, 3, 4 and 5 responders out of 12 subjects. Assuming the

true ORR is 25%, 12 subjects can provide approximately 84% probability to observe at least 2 responders.

Table 5-1: Probability of observing responses given true ORR for sample size of 23 subjects

True ORR	Probability of observing 0,1 or 2 responses	Probability of observing ≥ 3 responses
5%	89.5%	10.5%
20%	13.3%	86.7%
30%	1.6%	98.4%

Table 5-2: Two-sided 95% exact CI using Clopper-Pearson method based on number of observed responses out of 23 subjects

The number of observed responses	3	4	5
Observed Response Rate	3/23 (13.0%)	4/23 (17.4%)	5/23 (21.7%)
95% exact CI	(2.8%, 33.6%)	(5.0%, 38.8%)	(7.5%, 43.7%)

Table 5-3: Two-sided 95% exact CI using Clopper-Pearson method based on the number of observed responses out of 12 subjects

Number of observed responses	1	2	3	4	5
Observed Response Rate	1/12 (8.3%)	2/12 (16.7%)	3/12 (25.0%)	4/12 (33.3%)	5/12 (41.7%)
95% exact CI (%)	(0.2, 38.5)	(2.1, 48.4)	(5.5, 57.2)	(9.9, 65.1)	(15.2, 72.3)

2) Recurrent/Metastatic Combination Cohort:

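### Two neoadjuvant detection probabilities are slightly overstated at n=21, and the supplied documents assign no confidence interval to the primary AE/SAE incidence (minor)

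*Protocol*

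**What the plan says.** On size, Protocol 8.1 states: "The SCCHN tumor types will contain 21 HPV-positive and 21 HPV-negative evaluable subjects"; and "MCC and cervical, vaginal, or vulvar cancers tumor types will contain 21 evaluable subjects each". It says that sizing is not power-based and describes what 21 delivers: "A sample size of 21 can detect, with more than 66% and 89% probability, a safety event" at true rates of 5% and 10%. The Protocol synopsis repeats this: "A sample size of 21 subjects can detect, with more than 66% and 89% probability, a safety event". For pCR rates of 10%, 15% and 20%, SAP Section 5 states that "a sample size of 21 can detect, more than 89%, 97% and 99% probability, at least one pathologic complete response"; the synopsis and Protocol 8.1 give the same percentages.

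On analysis, Hypothesis A (Protocol 1.2) is that "Nivolumab, in the neoadjuvant setting, will be safe and tolerable". Protocol 8.3.1 and SAP 4.1.1 name two kinds of neoadjuvant primary endpoint: the incidence of drug-related select AEs and drug-related SAEs, and the rate of surgery or chemoradiation delay beyond 4 weeks due to a drug-related AE. Delay receives a two-sided 95% Clopper-Pearson interval in Protocol 8.4.2.1, Protocol 8.4.3 and SAP 7.5.1.1. For the AE endpoint, Protocol 8.4.2.1 only points onward: "Analyses of drug-related select AEs and drug-related SAEs are discussed in" Section 8.4.3. That section says that "drug-related SAEs will be tabulated using worst grade per NCI CTCAE version 4 criteria", by organ class and preferred term. SAP 7.6, including 7.6.2 (serious AEs) and 7.6.6 (select AEs), refers to the Core Safety SAP.

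**The concern.** The detection probabilities are the only quantitative support given for 21 subjects per tumor type. They are worded as lower bounds, so each should be met at n=21. Two are not.

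The second matter is how a low event count will be read. A 5% event is absent from 21 subjects about one time in three, so few or no events is weak evidence of safety unless the report also states which rates remain compatible with the data. The plan gives that information for delay. As supplied, it does not say that it will be given for AE and SAE incidence, although that is also a primary endpoint.

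**Working it through.** **Inputs.** n=21 per tumor type (Protocol 8.1, SAP 5). Event rates of 5% and 10% for safety, and 10%, 15% and 20% for pCR (same sections). Interval method: two-sided 95% Clopper-Pearson (Protocol 8.4.2.1; SAP 7.1 and 7.5.1.1).

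**Step 1: reproduce the plan's figures.** The probability of at least one event in n subjects is 1 − (1 − p)^n. At n=21:

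| True rate p | Plan: probability exceeds | (1 − p)^21 | 1 − (1 − p)^21 | Met? |
|---|---|---|---|---|
| 5% (safety) | 66% | 0.34056 | 65.94% | No, short by 0.06 points |
| 10% (safety and pCR) | 89% | 0.10942 | 89.06% | Yes |
| 15% (pCR) | 97% | 0.03295 | 96.7% | No, short by about 0.3 points |
| 20% (pCR) | 99% | 0.00922 | 99.08% | Yes |

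All four match the plan when rounded to a whole percent, so the method is the plan's own. The two failures come from rounding up and then describing the rounded value as exceeded. With n=22 the 5% figure is 67.65% and the 15% figure is 97.20%, so both statements are true from 22 subjects onward.

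**Step 2: what a zero count leaves open.** The chance of no event in 21 subjects is 34.1% at a true rate of 5% and 10.9% at 10%. With no events, the two-sided 95% Clopper-Pearson upper limit is 1 − 0.025^(1/n). For n=21 this is 1 − 0.025^(1/21) = 16.1%. The upper limits for 1, 2 and 3 events in 21 are 23.8%, 30.4% and 36.3%.

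**Step 3: sensitivity to the denominator.** The 21 are evaluable subjects, meaning treated subjects with paired Screening and Day 29 tissue (Protocol 8.2). Safety is analysed in all treated subjects (Protocol 8.4.3), so the safety denominator may be larger. At n=22 a 5% event is absent with probability 32.4%, and the upper limit for zero events is 1 − 0.025^(1/22) = 15.4%. The message does not change.

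**Step 4: which endpoint has an interval.** Delay has one in three places. For AE and SAE incidence, Protocol 8.4.3 specifies descriptive tabulation and SAP 7.6 refers elsewhere. SAP 7.1 says that intervals for binomial proportions use Clopper-Pearson; it fixes the method, not the list of endpoints that receive an interval.

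**The case against.** **The arithmetic is only rounding.** This stands. No sample size, endpoint or decision depends on 0.06 or 0.3 points, and the 15% figure concerns pCR, an exploratory endpoint, so it has no bearing on safety. One treated subject without paired tissue would bring the safety denominator to 22, where the 66% statement holds. What remains is that the statements are made about 21 and are not true at 21.

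**The interval may already be planned.** SAP 7.1 could be read to cover AE proportions, and the Core Safety SAP may specify a limit. Neither can be excluded from the documents supplied. Protocol 8.4.3 does not mention select AEs by name, so it cannot show that they will only be tabulated. The supportable statement is that no supplied passage assigns an interval to this endpoint.

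**Stronger readings that the documents do not support.**
- A reader might infer that the whole neoadjuvant safety objective lacks an upper limit. It does not: delay is a primary endpoint with an exact interval, and Protocol 3.1.2 closes a tumor type if at least 3 of the first 10 subjects have a delay beyond 4 weeks due to a label-specified immune-related event. That rule does not bound SAE or select-AE incidence, because an event that causes no such delay does not count towards it.
- A reader might apply the roughly 3% drug-related SAE frequency in Protocol 1.1.3 to 21 subjects and conclude that zero SAEs is the likely result. That frequency covers the first 4 weeks of treatment, whereas SAP 6.1.2 counts events to 30 or 100 days after the last dose. The windows do not match.
- A reader might infer that safety will be declared if no event is seen. No passage sets such a rule. A limit can also be calculated afterwards from any reported count and denominator, so what is missing is pre-specification, not information.

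**Conclusion.** Both parts hold, and both are minor. At n=21 the detection probabilities are 65.9% for a 5% safety event and 96.7% for a 15% pCR rate, slightly below what the synopsis, Protocol 8.1 and SAP 5 state; the other figures are right. This rests on independent subjects with a common event rate, the assumption under which the plan's own figures reproduce.

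Of the two kinds of neoadjuvant primary safety endpoint, one has a specified interval. The other, drug-related select AE and SAE incidence, has none in the documents supplied, subject to what the Core Safety SAP says. The size of the gap is illustrated by the 16.1% upper limit for 0/21, which is the context a low count needs. None of this shows that the cohort is the wrong size or that the safety objective is unbounded.

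**What to change.** 1. In the Protocol synopsis, Protocol 8.1 and SAP 5, restate the probabilities as 65.9% and 89.1% for 5% and 10% safety events, and as 89.1%, 96.7% and 99.1% for pCR rates of 10%, 15% and 20%.
2. In Protocol 8.4.3 and SAP 7.5.1/7.6, state that drug-related SAE incidence and drug-related select AE incidence will be reported for each neoadjuvant tumor type, in all treated subjects, with the two-sided 95% Clopper-Pearson interval already used for surgery delay. Cite the upper limit in the safety conclusion. If the Core Safety SAP already provides this, a specific cross-reference is enough.

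The cost is a wording change in three places and one column in the neoadjuvant safety tables. No extra subjects, data or visits are needed. Two stated probabilities become marginally less favourable.

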Each dosing schema will contain approximately 40 subjects. With Revised Protocol 06, no new subjects will be randomized in the anogenital HPV associated tumors cohorts.

Additionally, the metastatic cervical Combination B cohort will be expanded to treat approximately 50 subjects as first-line treatment for their recurrent/metastatic disease if unfit or unsuitable to receive platinum-based therapy and approximately 20 subjects as second-line treatment for their recurrent/metastatic SCC of the cervix to confirm the efficacy signal. With Combo B and the Combo B expansion, there should be a total of approximately 75 subjects with first-line treatment and approximately 35 subjects with second-line treatment of cervical cancer (approximately 110 cervical subjects total).

The HPV+ SCCHN with prior PD-1/PD-L1 treatment tumor type will be enrolled in Metastatic Combination Cohort (Combo C). Combo C will contain approximately 40 subjects. However, at Revised Protocol 05, no new subjects will be enrolled in this cohort.

Approximately 40 HPV negative and HPV indeterminate I-O naive SCCHN subjects will be enrolled to the Combo D treatment arm. With Revised Protocol 06, no new subjects will be enrolled in this cohort.

Sample sizes of each treatment arm in each tumor type are summarized in [Table 8.1-3](#).

An ORR in excess of 10% will be considered of clinical interest. Assuming the true ORR is 25%, 40 subjects in each tumor type can provide approximately 79.8% power to reject the null hypothesis that the true ORR is 10%, considering a 2-sided alpha of 5%. In addition [Table 8.1-4](#) shows the precision of the estimation of ORR based on the two sided 95% exact CI using Clopper-Pearson methods based on 8, 9, 12, 16 and 20 responders out of 40 subjects. At observed more than or equal to 9 responders, ie, $ORR \geq 22.5\%$, the lower bound of the 95% CI excludes 10%.

[Table 8.1-5](#) shows the precision of the estimation of ORR based on the two sided 95% exact CI using Clopper-Pearson methods based on 1, 2, 3, 4 and 5 responders out of 12 subjects. Assuming the true ORR is 25%, 12 subjects can provide approximately 84% probability to observe at least 2 responders.

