In this study, an ORR in excess of 10% will be considered of clinical interest. Assuming the true ORR is 25%, 40 subjects in each tumor type can provide approximately 79.8% power to reject the null hypothesis that the true ORR is \leq 10%, considering a two-sided alpha of 5%. In addition, Table 5-5 shows the precision of the estimation of ORR based on the two-sided 95% exact CI using Clopper Pearson methods based on 8, 9, 12, 16 and 20 responders out of 40 subjects. At observed more than or equal to 9 responders, i.e., $ORR \geq 22.5\%$, the lower bound of the 95% CI excludes 10%.

Table 5-6 shows the precision of the estimation of ORR based on the two-sided 95% exact CI using Clopper-Pearson methods based on 20, 22, 26, 30, 33, and 35 responders out of 50 subjects.

At observed more than or equal to 22 responders, i.e., $ORR \geq 44\%$, the lower bound of the 95% CI excludes 30%; at observed more than or equal to 26 responders, i.e., $ORR \geq 52\%$, the lower bound of the 95% CI excludes 37%.

Table 5-7 shows the precision of the estimation of ORR based on the two-sided 95% exact CI using Clopper-Pearson methods based on 3, 5, 8, 10, 12 and 14 responders out of 35 subjects. At observed more than or equal to 8 responders, i.e., $ORR \geq 22.9\%$, the lower bound of the 95% CI excludes 10%.

Due to the low prevalence of EBV+ Gastric tumor types and the current investigation of this tumor type in other BMS-sponsored studies, combination cohorts in this study will no longer include EBV+ Gastric tumor type.

Table 5-5: Two-sided 95% exact CI using Clopper-Pearson method based on the number of observed responses out of 40 subjects

Number of observed responses	8	9	12	16	20
Observed Response Rate	8/40 (20.0%)	9/40 (22.5%)	12/40 (30.0%)	16/40 (40.0%)	20/40 (50.0%)
95% exact CI (%)	(9.1, 35.6)	(10.8, 38.5)	(16.6, 46.5)	(24.9, 56.7)	(33.8, 66.2)

Table 5-6: Two-sided 95% Exact CI Using Clopper-Pearson Method Based on the Number of Observed Responses out of 50 Subjects

Number of observed responses	20	22	26	30	33	35
Observed Response Rate	20/50 (40.0%)	22/50 (44%)	26/50 (52%)	30/50 (60%)	33/50 (66%)	35/50 (70%)
95% exact CI (%)	(26.4, 54.8)	(30.0, 58.8)	(37.4, 66.3)	(45.2, 73.6)	(51.2, 78.8)	(55.4, 82.1)

Table 5-7: Two-sided 95% Exact CI Using Clopper-Pearson Method Based on the Number of Observed Responses out of 35 Subjects

Number of observed responses	3	5	8	10	12	14

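### The 79.8% power quoted for 40 subjects per tumor type is a normal-approximation figure; with the exact interval the plan uses (at least 9 of 40 responders), power is 70.0%

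*Protocol*

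**What the plan says.** For the recurrent/metastatic combination cohorts, Protocol 8.1 makes two statements in one paragraph. The first is a power claim: "Assuming the true ORR is 25%, 40 subjects in each tumor type can provide approximately 79.8% power to reject the null hypothesis", the null being an ORR of 10%, "considering a 2-sided alpha of 5" percent. The second concerns the exact interval: "At observed more than or equal to 9 responders" (22.5%), the lower 95% limit lies above 10%. Table 8.1-4 supports the second statement, with intervals of 9.1% to 35.6% at 8/40 and 10.8% to 38.5% at 9/40.

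Protocol 8.4.2.1 has ORR summarized by response rates and their "corresponding two-sided 95% exact CIs using Clopper-Pearson method". SAP 7.1 and 7.5.1.2 specify the same method. SAP Section 5 repeats the power figure ("40 subjects in each tumor type can provide approximately 79.8% power to reject the null hypothesis", with the null written as at most 10%), and so does the Synopsis. None of the three places names the test behind 79.8%. Both documents also open the sample size section by saying that the size was not set by a power calculation.

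**The concern.** The power figure and the responder threshold stand side by side, so a reader takes 79.8% as the chance of seeing at least 9 of 40 responders when the true ORR is 25%. The two do not fit together: the threshold comes from the exact interval and the power does not.

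The values 10% and 25% are the study's own benchmarks for clinical interest and strong clinical interest (Protocol 8.3.1), and ORR is the primary endpoint of every metastatic cohort. Table 8.1-3 lists eight cells of 40 subjects. Anyone looking at such a cell with 8 or fewer responders, and relying on the stated power, would put the chance of having missed a true 25% ORR at about one in five. If the exact calculation is right, it is three in ten.

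**Working it through.** **Inputs, all from Protocol 8.1**

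- Null ORR p0 = 0.10 ("the null hypothesis that the true ORR is 10" percent)
- Alternative p1 = 0.25 ("Assuming the true ORR is 25" percent)
- n = 40 ("40 subjects in each tumor type")
- Two-sided alpha 0.05, so 0.025 in the upper tail and z = 1.96

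**Step 1. Reproduce the plan's figure.** Take the one-sample normal formula with the null variance in the critical value, the alternative variance in the power, and no continuity correction:

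Power = Φ( [p1 − p0 − z·√(p0(1−p0)/n)] / √(p1(1−p1)/n) )

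- Numerator: 0.15 − 1.96 × √(0.09/40) = 0.15 − 1.96 × 0.04743 = 0.0570
- Denominator: √(0.1875/40) = 0.0685
- Ratio: 0.833, and Φ(0.833) = 0.7976

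This rounds to the stated 79.8%. Other approximations at the same alpha do not match: with continuity correction 74.2%, alternative variance only 59.1%, null variance only 88.5%, arcsine 72.3%.

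**Step 2. Confirm the exact threshold.** The Clopper-Pearson lower 95% limit with x responders is the 2.5th percentile of a Beta(x, n − x + 1) distribution.

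- 8/40: 9.05%, so 10% is not excluded
- 9/40: 10.84%, so 10% is excluded

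The threshold of 9 in Protocol 8.1 is correct.

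**Step 3. Exact power and error at each cut-off**, from P(X ≥ r) with X binomial(40, p):

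| Cut-off | P at ORR 10% (upper-tail error) | P at ORR 25% (power) |
|---|---|---|
| at least 8/40 | 4.19% | 81.8% |
| at least 9/40 | 1.55% | 70.0% |
| at least 10/40 | 0.51% | 56.0% |

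No cut-off gives 79.8%. The cut-off that corresponds to the planned interval gives 70.0%.

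**Step 4. Size of the gap.**

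- Power: 79.8 − 70.0 = 9.8 points
- Type II error: 100 − 70.0 = 30.0%, against an implied 100 − 79.8 = 20.2%; the ratio is 30.0/20.2 = 1.49
- Solving P(X ≥ 9) = 0.798 for the true ORR gives about 27.2%, so the stated power applies to a true rate about 2 points above the one named

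**Step 5. Compare with neighbouring figures.** Other probabilities in the same section are exact binomial. The 84% for at least 2 responders in 12 at ORR 25% is 84.2% exactly. The 89.5% in Table 8.1-1 for 2 or fewer of 23 at ORR 5% is also exact. A reader has no cue that 79.8% was obtained differently.

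**The case against.** Four points can be made for the plan.

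1. **At least 9 of 40 is never labelled a decision rule.** It describes the precision table, and the analysis sections specify an interval, not a test. This is true. But the power claim speaks of rejecting a null hypothesis, and the exact interval is the only ORR inference in either document. No other rejection criterion is offered.

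2. **79.8% is a fair approximation for a score z test.** That test would reject at 8/40 (z = 2.11), and its exact power is 81.8%, about 2 points from the stated figure. So this is a mismatch of method, not a slip in arithmetic. That description is fair, but it does not rescue the number. The z test is not planned. It would reject at 8/40, where Table 8.1-4 shows an interval that contains 10%. Its upper-tail error of 4.2%, plus 1.5% for the 0/40 outcome, comes to 5.7%, above the stated two-sided 5%.

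3. **The sample size does not rest on power.** Both documents say so, the study is non-comparative, and no stopping or go/no-go rule for these cells uses the figure. This stands, and it limits the consequences: no enrolment target or reported interval changes. It does not make a published power figure correct.

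4. **The scope is narrower than eight cells.** Combo C closed to enrolment at Revised Protocol 05, and Combo D and the anogenital cells at Revised Protocol 06, so those cells may fall short of 40. Cervical Combo B, expanded to about 110, has its own tables. In practice the statement bears mainly on the Combo A cells. This also stands.

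**Conclusion.** The concern holds. For 40 subjects, a null ORR of 10% and a true ORR of 25%, the probability that the planned two-sided 95% Clopper-Pearson interval excludes 10% from below is 70.0%, with an upper-tail error of 1.55%. The stated 79.8% overstates it by 9.8 points and understates the type II error by about a third (20.2% against 30.0%).

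The conclusion takes rejecting the null to mean that the planned exact interval lies above 10%, which is the only criterion the documents give. The normal-approximation origin of 79.8% is inferred from the match to the first decimal, since no test is named; the 70.0% does not depend on that inference. The word approximately does not cover a gap of this size in a figure given to one decimal. The effect on the conduct and reporting of the trial is small; the effect on how a cell with few responders is read is the reason to correct it.

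**What to change.** In the Synopsis, Protocol 8.1 and SAP Section 5, replace the 79.8% with approximately 70% power, and state the basis: exact binomial, 10% excluded when at least 9 of 40 respond, upper-tail error about 1.5%. If the sponsor wants to keep 79.8% for continuity, it should be labelled a normal approximation and the exact 70% given beside it; the label alone would leave the figure out of line with the planned interval.

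The cost is a wording change in three places and a less favourable figure. Because the sample size is not based on power, no patients need to be added and no endpoint, analysis or table changes.
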